Specific Aim 1. Effects of stress on maternal antibody responses will be tested independently for each vaccination year. Thus, our data will provide valuable data regarding the extent to which effects of stress are consistent and reproducible across flu seasons. We will test the association between obesity and maternal antibody responses using data across all three vaccination years. The primary and supporting endpoints will be the same as above. The independent variable will be obesity status. A secondary analysis will explore the interaction between obesity and stress; these analyses will focus on depressive symptoms and the composite stress measure (CES-D, PSS, and STAI). We expect that stress and obesity will interact, with more pronounced effects of obesity among the highly stressed. Although the study is not specifically powered for the detection of interaction effects, based on our preliminary findings we expect to obtain useful estimates.

Specific Aim 2. The primary analysis will be logistic regression testing whether stress and obesity are associated with attenuated cord blood antibody levels. The primary endpoint will be adequacy of cord blood antibody level (yes/no), with an adequate antibody level defined as a serum HAI antibody titer > 40 . The same models will be used as described in Specific Aim 1, except for the change in dependent variable. A supporting analysis will test cord blood antibody levels as a continuous measure. Linear regression models will be used to test this supporting outcome, using the same independent variables as the logistic regression models.

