Secondary mediational analyses will examine four potential pathways linking stress and obesity with low cord blood antibody titers: 1) the magnitude of maternal response at one month post-vaccination, 2) the maintenance of maternal antibody levels over time (maternal antibody at one month post-vaccination / maternal antibody at delivery) controlling for weeks from vaccination to delivery, 3) efficiency of antibody transfer (ratio of maternal antibody at time of delivery / newborn antibody level), and 4) the frequency of preterm birth (expected to be 15% overall). We expect factors 1 & 3 to exert the greatest effects. Our study is powered to detect overall effects of maternal stress and obesity on newborn antibody levels, but is not powered to detect the relative influence of each of these specific pathways. However, these analyses will provide a critical foundation for future studies in this line of investigation which will include this focus.

We do not expect racial differences in Aim 1. Due to higher rates of preterm birth in Blacks than Whites (18% vs 12%), this pathway is likely to contribute more strongly to the association between stress and lower cord blood titers for Blacks. We will use two approaches to examine effects of race: 1) inclusion of race as a predictive variable and 2) testing the secondary analysis model above separately for Blacks and Whites.

References

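### The maintenance and transfer-efficiency mediators run opposite to their names, and a joint fit of all four mediators, which the plan leaves open, would force the preterm-birth pathway to zero

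*Combined protocol and SAP*

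**What the plan says.** Section III.E (Data Analysis), in the paragraph after Specific Aim 2, lists four candidate pathways from stress and obesity to low cord blood titres:

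1. the size of the maternal response at one month;
2. "the maintenance of maternal antibody levels over time (maternal antibody at one month post-vaccination / maternal antibody at delivery"), with the added condition "controlling for weeks from vaccination to delivery";
3. "efficiency of antibody transfer (ratio of maternal antibody at time of delivery / newborn antibody level");
4. preterm birth, expected in 15% overall.

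Pathways 1 and 3 are expected to matter most. The plan says that the study "is not powered to detect the relative influence of each of these specific pathways", but presents the results as groundwork for later studies.

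The outcome is the cord titre. Specific Aim 2 treats it as adequate or not (titre above 40) and adds: "A supporting analysis will test cord blood antibody levels as a continuous measure".

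The race paragraph gives preterm rates of 18% in Black and 12% in White women and predicts that "this pathway is likely to contribute more strongly to the association between stress and lower cord blood titers for Blacks". One of its two approaches is "testing the secondary analysis model above separately for Blacks and Whites".

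No model is written out. The text gives neither the scale of the ratios nor whether the mediators enter one model or four.

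**The concern.** There are two linked problems.

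First, both ratios are upside down relative to their names. One-month over delivery grows as antibody is lost, and maternal over newborn grows as transfer fails. Someone reading only the labels in a results table would conclude that stress improves maintenance or transfer when the data show the reverse. Pathway 3 is one of the two that the plan expects to be strongest, so its sign will be looked at.

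Second, the newborn titre is the denominator of mediator 3 and is also the outcome. If mediator 3 shares an outcome model with preterm birth, any effect of preterm birth that works through poorer transfer is held fixed. If mediators 1 and 2 are in that model as well, nothing is left for preterm birth to explain. Pathway 4 could then be reported as null because of the model rather than the data. It is also the only pathway for which the plan makes a prediction by race.

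**Working it through.** The plan gives no figure to reproduce here. The check has four steps.

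**Notation.** M1 is the maternal titre at one month, Md the maternal titre at delivery, C the cord (newborn) titre. As defined in section III.E, maintenance = M1/Md and efficiency = Md/C.

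**Step 1: direction (illustrative titres).**

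| M1 | Md | Maintenance M1/Md | Share kept Md/M1 |
|---|---|---|---|
| 160 | 160 | 1 | 1 |
| 160 | 80 | 2 | 0.5 |
| 160 | 40 | 4 | 0.25 |

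| Md | C | Efficiency Md/C | Share transferred C/Md |
|---|---|---|---|
| 80 | 40 | 2.0 | 0.5 |
| 80 | 80 | 1.0 | 1.0 |
| 80 | 120 | 0.67 | 1.5 |

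Both scores rise as the named property gets worse.

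**Step 2: does the direction change the mediation result?** Since log(Md/C) = −log(C/Md), inverting a logged ratio reverses the stress-to-mediator path and the mediator-to-outcome path together, so their product is unchanged. A raw ratio and its reciprocal are not linearly related, so on the raw scale the fit changes. The size was checked in a large simulation. Assumed, per SD of stress on log2 titres: −0.3 on the one-month titre and −0.2 directly on transfer; odds ratio 1.5 for preterm birth; preterm birth lowering log2 transfer by 0.8; residual SD 1.0 for the one-month titre and 0.5 each for decay and transfer. From the plan: 15% preterm.

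- Stress effect on log2 transfer: −0.24 in total (−0.20 direct, −0.04 through preterm birth). On efficiency as defined it appears as +0.24.
- Indirect effect on log2 cord titre with logged ratios: −0.232 in either orientation.
- Indirect effect on log2 cord titre with raw ratios: −0.202 as written, −0.214 inverted.
- Indirect effect on raw cord titre with raw ratios: −10.3 titre units as written, −14.8 inverted (14.8/10.3 = 1.44). The absolute values depend on the assumed average titre.

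**Step 3: the identity.** C = M1 ÷ (M1/Md) ÷ (Md/C), so

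log C = log M1 − log(M1/Md) − log(Md/C).

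For example, with M1 = 160, Md = 80 and C = 40, on log2: 7.32 − 1 − 1 = 5.32 = log2 40.

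A linear model for log C with all four mediators (mediator 1 as the one-month level) therefore has coefficients 1, −1 and −1 on the three titre terms, 0 on preterm birth, and R-squared of 1. Titre error does not alter this, because the ratios are built from the same measured values. It holds in any subgroup, so also in each race-specific fit. For the above-40 endpoint, the matching logistic model separates perfectly and cannot be estimated.

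**Step 4: size of the blocking.** A second simulation used 400,000 records per setting, OLS on log2 cord titre, and these assumptions: stress −0.3 on the one-month titre, stress log-odds slope 0.6 for preterm birth, transfer SD 0.5, titre error SD 0.3. Preterm coefficient:

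| Assumed preterm effect on log2 cord titre | Mediators 1, 2 and 4 | All four, mediator 1 = level | All four, mediator 1 = fold rise |
|---|---|---|---|
| −0.4, all through transfer | −0.40 | 0.000 | −0.002 |
| −0.8, all through transfer | −0.80 | 0.000 | −0.009 |
| −1.2, all through transfer | −1.19 | 0.000 | −0.006 |
| −0.8, half through transfer | −0.48 | 0.000 | −0.013 |

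With transfer SD varied from 0.25 to 1.0, the fold-rise column stays between −0.016 and +0.005. With raw ratios in a four-mediator fit, an effect of −0.8 came out as −0.016. With preterm birth as the only mediator, an effect of −0.8 was recovered as −0.80 to −0.81. An effect of −0.8 on log2 is a cord titre multiplied by 2^(−0.8) = 0.57.

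In the last row, −0.48 rather than −0.8 appears without the transfer ratio because the maintenance ratio absorbs part of the effect.

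**The case against.** The strongest reply is that little depends on this. The analyses are labelled secondary, the plan disclaims power for individual pathways, and both ratios are printed with numerator and denominator, so a careful analyst will read the signs correctly. On logs, the natural scale for titres, the indirect effect is the same either way. The blocking needs a joint fit that the plan never states: the singular "model" in the race paragraph and the mention of relative influence lean that way, but attaching the weeks covariate to mediator 2 alone leans towards separate fits. Even in a joint fit the preterm coefficient is correct as an effect given transfer. Inverting the ratio does not remove the cord titre from it.

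Most of this stands, and it sets the weight of the point. Three things remain:

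- The definitions as written contradict their labels, whatever the scale.
- Low power makes an estimate imprecise, whereas conditioning on transfer changes what is estimated at every sample size.
- A coefficient given transfer is not the contribution of pathway 4, which is what the plan wants to learn.

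The remark about the cord titre is also right, and the fix has to deal with it.

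**Conclusion.** The point holds as a minor one. That both ratios are inverted follows from the text alone. The zero preterm coefficient is algebra, conditional on three things: all four mediators in one model, log scale, and the newborn titre in the ratio being the same measurement as the outcome. With fold rise as mediator 1, or with raw ratios, it is close to zero rather than exactly zero. The other sizes rest on assumed effects and show direction and order of magnitude only.

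Four stronger readings are tempting, and the documents do not support them:

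- *The plan hides the preterm pathway.* It does so only under a joint fit, and the text does not say which fit is meant.
- *The inverted ratios invalidate the mediation results.* On logs the indirect effects are untouched.
- *A joint fit would make preterm birth look protective.* That can arise if only efficiency and preterm birth are fitted together and the plan's weeks covariate is left out. With weeks added the coefficient is about zero, and with all four mediators it is zero by identity.
- *Aim 2 is compromised.* Its primary test contains none of these mediators.

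**What to change.** Amend the mediational paragraph of section III.E as follows:

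- Define maintenance as log(delivery titre / one-month titre) and transfer efficiency as log(newborn titre / maternal titre at delivery), so that higher means better.
- State whether the mediators are fitted jointly or one at a time.
- Estimate the preterm pathway, overall and in the race-specific fits, in a model that leaves out the transfer ratio. Say whether maintenance stays in that model, since it absorbs any preterm effect on the maternal delivery titre.
- Because the corrected transfer ratio still contains the cord titre, interpret transfer by regressing it on stress and obesity as an outcome.
- State that the indirect effects of pathways 3 and 4 are not to be added.

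The cost is wording and some reanalysis; no new data are needed. The downsides are that results are on the log-titre scale and that pathways 3 and 4 overlap, because part of the stress effect on transfer may run through preterm birth. Estimates of pathway 4 will stay imprecise: 180 × 0.15 = 27 preterm births are expected in all, and fewer in each race-specific fit.
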